The "Procedure" CRF will be used to collect data about the ablation procedure and discharge from the medical center. Information regarding anticoagulation therapy, procedure summary information, sedation and consumables, PVI confirmation, cardiovascular medication, date and status at hospital discharge is to be collected. Verification of study defined AEs will be done during the procedure and at the moment of hospital discharge.

If the attempt to conduct Phased RFA ("index" procedure) is not successful for clinical or technical reason, patients will stay enrolled into the registry. If Phased RFA is repeated ("repeated" procedure) or re-do due

to arrhythmia recurrence, the “procedure” CRF should be filled in. Information about all Phased RFA attempts will be used for the analysis. If patient has re-do procedures with some other technology than Phased RFA, Procedure CRF is not required; information about technology which was used for re-ablation to be collected in eCRF “General FU”.

During the Phased RFA, the investigator may require use of other commercially available devices for other ablations such as Afi/LAT or other AF triggers. The use of other devices will be at the investigator’s discretion and use will be documented on the eCRF.

Hospital discharge needs to be completed when the patient is discharged from the hospital, this data to be collected as a part of the procedure visit. Information about date of discharge, reportable adverse event since the procedure and recommended medication information is to be collected. Post-ablation drug regimen is determined at clinical discretion of the treating investigator.

General Follow up visits (in hospital)

The “General” FU CRF will be used to collect data during all standard visits at the site within the following 12 months after the index or study procedure. Data to be collected include: arrhythmia assessment, diagnostics, symptoms, hospitalizations, ablation information and medication. If “General FU” will take place due to system/procedure related AE, “Adverse Event” CRF should be filled in additionally to the “General” FU CRF.

If at any moment during FU, the patient withdraws PIC/PDRF or PI receives information about the patient’s death, the “Exit” CRF should be filled in addition to the “General FU” CRF. All data collected prior to the patient exit will be used for analysis, unless different is required by local laws and regulations.

12 months FU (in hospital or by phone)

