7.2.1 Frequency of Follow up

Data collection will be completed following standard of practice procedures at each participating site. Most of the sites have a standard of care for post AF ablation visits to invite patients for the medical checkup after the "blanking period" which is lasts around 3 month after the ablation procedure; some sites also see patients at 6 and 12 months after the Phased RFA.

To mitigate variations in clinical care practices for analysis, the visit windows below are proposed to aligning with typical care practices for this therapy. Data analyses will include follow up visits, regardless of when they occur.

Table 7-2: Follow Up Visit Windows

| Months | Window Starts (days post procedure) | Target (days post-procedure) | Window end (days post-procedure) |
|-----------|-------------------------------------|------------------------------|----------------------------------|
| 3 months | 85 | 90 | 100 |
| 6 months | 175 | 180 | 190 |
| 12 months | 351 | 365 | 425 |

Additional data collection activities may be completed using sub-studies under the GOLD AF Registry protocol. Sub-studies may be developed to satisfy local data needs and/or evaluate additional areas of scientific interest. Sub-studies must be reviewed and approved by Medtronic and will be documented and managed under separate cover.

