### 7.2.3 Follow-up data

Only unique 12MFU form per patient will be used for analysis. If a General Follow-up visit meets the time window of the 12MFU visits (>351d after procedure), manually data review and selection will be performed. Any FU forms older than 440 days after procedure will not be used for analysis (protocol deviation). For patients with contradictory information in the eCRF the following rules are applied:

1. 12 month FU (by phone or visit) is preferred to GFU.
2. Events are always kept, even if GFUs are discarded.

The decision on patient level is given in Appendix F.

12MFU visit and 12MFU by phone results will be analysed combined, where variables were recorded in a similar manner (demographics, symptoms, hospitalization, medication). Not combinable information will be shown separately.

General FU (GFU) data will be assigned to the respective time period after first documented procedure:

- 0 to 3 months (1 day <= time between procedure and GFU <= 90 days)
- 3 to 6 months (90 days < time between procedure and GFU <= 180 days)
- 6 to 9 months (180 days < time between procedure and GFU <= 270 days)
- 9 to 12 months (270 days < time between procedure and GFU <= 351 days)

Multiple GFU per patient within one time period will be shown separately in chronological order (i.e. all first GFUs in one time period, all second GFUs in one time period and so on) as descriptive tables.

Number of GFUs per time period and time (days) until GFU during the time period (for each visit per time period) will be shown. Event rates for clinical events (history of AF, re-ablations and hospitalizations) will be calculated for 3, 6 and 9 months after discharge exactly using appropriate statistical methods.

Predefined time windows for GFU from CIP Version 2.0, Table 7.2 will not be applied.

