## 8.1 Statistical analyses for the main objective

### 8.1.1 Estimate Phased RFA 12 month success rate

Success rate estimated as the time to first AF re-occurrence event from the first documented procedure. Data about AF events will be collected since the first documented procedure, including 90 days of the "blanking period" and closes at 12 months FU. If no AF events occur during the follow-up period (considering the "blanking period") up to 12 (+2) months, the case is considered to be "event-free". Calculations will be done for exact 12 months (351 days) after first documented procedure.

Main objective will be calculated for the BAS, FAS and EFAS (see chapter 4 and Appendix B). A successful first documented procedure (successfulness by PVI confirmation) is the basis to calculate the main objective. Patients with a procedure during the "blanking

---

 in the service agreement #2 refers to the final report, which is one and the same document for this study

period" of 90 days after first documented procedure will be excluded from main objective calculations.

Predefined AF re-occurrence definition from CIP Version 2.0 will not be applied to calculate the main objective. Further analysis might be used to estimate Phased RFA success rate considering (re-)occurring left Afl events.

AF re-occurrence event defined as:

- AF pharmacological and/or electrical CV
- AF more the 30 sec on ECG/EGM
- AF less than 30 sec in combination with AF symptoms
- Re-ablations for AF

For this analysis adjudicated AE data and coded AE data (free text fields) will be used. AF re-occurrence event rate will be estimated with and without the use of antiarrhythmic drugs at time of the 12 month follow-up. AF re-occurrence rates will be calculated for patients from BAS and FAS (Appendix B) which need to have a signed 12 month FU / 12 month FU by phone form by definition. AF re-occurrence is defined as the first event of AF re-occurrence event and their related date information based on the following eCRF forms and data fields:

**Table 4:** Main objective variables at 12MFU / General FU form

eCRF field	Related date field	Related FID's annotated eCRF (V1.3, V1.4)
Reason for visit: AF re-occurrence	Date of visit	F11000050 F11000010
Re-ablation reason: Due to AF- occurrence	Date of visit	F11000070 F11000010
History of arrhythmias since last visit: AF	Date of first occur- rence	F12000012 F12000050

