### 8.1.2 Methodology for analysing the main objective

Any AF re-occurrence event (Tables 5, 6 and 7) during the “blanking period” will be not be considered. “Blanking period” starts with the day of the first documented procedure and ends at exact 90 days. The first documented date of AF re-occurrence will be set as the event date. “Blanking period” for patients with additional procedure(s) at any time will not be started newly, they will be considered as “not-event free” at time of the first additional procedure.

Freedom from AF re-occurrence at 12 months will be estimated using Kaplan-Meier methods (time-to-first-event-analysis). A point estimate at the date of 12MFU post first documented procedure will be presented. Standard error will be approximated using

Greenwood's formula, and a two-sided 95% log-log confidence interval will be presented. For patients without a reported AF re-occurrence event, those patients will be censored. In this case, the right-censoring time will be set to the last study contact date. Main objective Kaplan-Meier estimation results will be displayed in percentages at 12 months (351 days) after first documented procedure. Estimated AF re-occurrence rates by month (at the end of month 3 to 11 after first documented-procedure) will be calculated and displayed as well. For group comparisons Log-Rank test will be applied. Also, Hazard ratios and 95% confidence intervals will be shown (for group comparisons, please see SAP chapter 8.6). For Kaplan-Meier estimation, numbers at risk will be displayed for reasonable points in time.

Re-occurrence of AF during 12 months (considering the "blanking period") will also be analysed via Cox proportional hazard regression model presenting hazard ratios and the corresponding 95% CI. Independent variables will be determined by Phased RFA procedure experts or physicians. Cox modelling for AF re-occurrence will be done for all pre-defined subgroups (FAS patients) where the analysis scope is the 12 month outcome (SAP chapter 8.6.1). Further Cox modelling (e.g. for multiple AF events) may be applied.

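### The SAP's with/without-antiarrhythmic-drug success rates, read as two strata, group patients by drug use at the 12-month contact, a variable that recurrence can drive

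*SAP*

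**What the plan says.** The drug split is in the SAP's main-objective section (8.1.1): "AF re-occurrence event rate will be estimated with and without the use of antiarrhythmic drugs at time of the 12 month follow-up". The protocol's main-objective section (4.4.1) has no such split.

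The timing comes from four places:

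- SAP 8.1.2: the blanking period "starts with the day of the first documented procedure and ends at exact 90 days", and events inside it are not counted.
- SAP 8.1.1: "Calculations will be done for exact 12 months (351 days) after first documented procedure".
- Protocol Table 7-2: the 12-month row reads "12 months | 351 | 365 | 425" (window start, target and window end, in days after the procedure).
- SAP 7.2.3: follow-up forms are used up to day 440.

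On drug treatment, Protocol 7.2 says: "Post-ablation drug regimen is determined at clinical discretion of the treating investigator". The event list in SAP 8.1.1 itself includes treatment of AF, for example "AF pharmacological and/or electrical CV".

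Two other parts of the SAP bear on the point. Table 2 compares antiarrhythmic medication at discharge with that at the 12-month contact. Appendix C defines two subgroups by whether an antiarrhythmic drug was taken at any point in the study, and SAP 8.1.2 plans Cox models for all predefined subgroups whose scope is the 12-month outcome.

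**The concern.** A rate estimated within groups is easy to interpret when membership is settled before the outcome is counted. Here membership is settled afterwards. A patient whose AF returns in month 5 may be put on a drug and still be taking it at the 12-month contact. A patient in stable rhythm may have stopped by then. Comparing the two groups then partly compares patients sorted by their own result.

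At stake is the meaning of the rate without drugs. It stands in the main-objective section, and a reader can easily take it as drug-free efficacy of the ablation. SAP 8.1.1 and 8.1.2 contain no safeguard: no landmark, no time-varying drug status and no composite definition. In addition, Baseline Analysis Set (BAS) patients without a 12-month form have no drug status at that contact, so they fall out of the split.

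**Working it through.** The plan states no figure for the two rates, so there is nothing to reproduce. The check is whether the split returns the true rate in a case where the truth is known.

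**Inputs**

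- Overall success 74%, so recurrence p = 0.26. Protocol 4.4.1 cites this as average chronic efficacy of the predecessor catheter.
- Drugs have no effect, so the right answer is 74% in both groups (assumption).
- q1 = share on drug at 12 months among patients with recurrence; q0 = the same share among patients without. **Neither is in the documents; the values below are assumptions.**

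**Formulas**

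- Success off drug = (1 − p)(1 − q0) / [(1 − p)(1 − q0) + p(1 − q1)]
- Success on drug = (1 − p)q0 / [(1 − p)q0 + p·q1]

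**Results (truth is 74% in every cell)**

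| q1 | q0 | Off drug | On drug |
|---|---|---|---|
| 0.30 | 0.30 | 0.518/0.700 = 74.0% | 0.222/0.300 = 74.0% |
| 0.40 | 0.30 | 0.518/0.674 = 76.9% | 0.222/0.326 = 68.1% |
| 0.40 | 0.20 | 0.592/0.748 = 79.1% | 0.148/0.252 = 58.7% |
| 0.60 | 0.20 | 0.592/0.696 = 85.1% | 0.148/0.304 = 48.7% |
| 0.20 | 0.30 | 0.518/0.726 = 71.3% | 0.222/0.274 = 81.0% |

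The split is unbiased only in the first row, where drug use does not depend on recurrence. In the last row, where patients with recurrence are less often on drug, the order reverses.

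**With a real drug effect.** Assume 40% are on drug at day 90, with later recurrence of 20% on drug and 30% off drug, and that 30% of the off-drug patients who recur then start a drug.

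- On drug at 12 months: recurrence = (0.4×0.2 + 0.6×0.3×0.3) / (0.4×0.2 + 0.6×0.3×0.3 + 0.4×0.8) = 0.134/0.454 = 29.5%
- Off drug at 12 months: recurrence = (0.6×0.3×0.7) / (0.6×0.3×0.7 + 0.6×0.7) = 0.126/0.546 = 23.1%

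Under these assumptions a protective drug appears harmful.

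**The composite for comparison.** Free of recurrence and off drug, over all patients, is (1 − p)(1 − q0): 0.74×0.8 = 59.2% for q0 = 0.20, 66.6% for q0 = 0.10 and 51.8% for q0 = 0.30. It describes how many patients are both event-free and off drug, and its denominator is not selected on the result.

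**The case against.** - **The sentence may not mean two strata.** It could mean two definitions of success: AF-free regardless of drugs, and AF-free while off drugs. The second is the composite and lacks this bias. This objection stands in part: the SAP does not say which is meant. At 74% success, q1 = 0.40 and q0 = 0.20, the two readings give 79.1% and 59.2%, so the text has to decide.
- **No passage says that recurrence leads to drug use.** Correct. A reader might infer that recurrence causes drug use at 12 months, so that the off-drug rate always overstates success. The documents support only that treatment is discretionary and so can respond to recurrence. The sign could be the other way, for example if patients who have a re-ablation, itself an event, more often end off drug.
- **The dependence will be visible.** Appendix D compares patients with and without re-occurrence on the 12-month tables, which include the medication list (Appendix B). The report should therefore show q1 and q0. This helps a careful reader, but it does not give the with/without rates in 8.1.1 a clear meaning.
- **The analysis is descriptive and supplementary.** True, and it limits the weight of the point. A descriptive rate can still mislead, and SAP 8.1.2 plans log-rank tests and hazard ratios for group comparisons.

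**Conclusion.** The point holds for the stratified reading: drug status is recorded at or after the end of the outcome window and can depend on the outcome. The two rates are then biased whenever that dependence exists.

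The size is not known. Under the assumed proportions with 74% success and no drug effect, the gap between strata runs from none (equal proportions), through 20.4 points (79.1% − 58.7%), to 36.4 points (85.1% − 48.7%). It reverses to −9.7 points (71.3% − 81.0%) when q1 = 0.20 and q0 = 0.30.

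A reader might also infer that the registry's main result is biased. It is not: the overall Kaplan-Meier estimate does not use drug status. The point concerns the with/without rates in 8.1.1 and, for the same reason, the Appendix C drug subgroups and any Cox model built on them. It should be corrected before the final analysis, but it does not undermine the main objective.

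**What to change.** Replace the sentence in SAP 8.1.1 with two statements:

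1. Any estimate stratified by antiarrhythmic drugs uses status at hospital discharge, which Table 2 already takes as its pre-value.
2. Drug-free success is a separate composite: free of AF re-occurrence and off antiarrhythmic drugs at the 12-month contact. All FAS patients are in the denominator, and the number of BAS patients without a 12-month form is stated. The definition of a documented 12-month form in SAP 4.3 does not require a medication list, so the number of FAS patients with missing drug status should be given too.

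For the two Appendix C subgroups defined by drug use at any point in the study, either redefine them by discharge status or label them descriptive only and leave them out of the Cox models.

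A day-90 landmark is not a good substitute. Visits before 12 months are unscheduled, and SAP 7.2.3 does not apply the Table 7-2 windows to general follow-ups, so drug status at day 90 is not systematically recorded.

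**Cost.** A few sentences in 8.1.1 and Appendix C, and no new data. There are two drawbacks. The discharge list is what was advised (Protocol 7.2: "reportable adverse event since the procedure and recommended medication information is to be collected"), so it does not reflect later drug use. The composite will also be lower than the off-drug stratum rate, for example 59.2% at 74% success and an assumed 20% drug use among event-free patients.

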3.4 Methodology

Patient can sign PIC/PDRF 14 days prior to the scheduled Phased RFA procedure to have sufficient time to consider the participation in the registry.

Observations will be documented at baseline, ablation procedure/hospital discharge and whenever patients visit the medical center with regard to AF recurrence, catheter ablations, Adverse Events, regular medical checkup etc.

Patient will be followed up for minimum 12 and maximum 14 months following first (hereafter "index") Phased RFA procedure. In case the index procedure is performed, but is not successful for medical or technical reasons, patients will stay in the registry until the end of the FU period.

Figure 3-5 provides an overview of the data entry flow chart. The process of data collection is described in Chapter 7. Furthermore, an overview of data to be collected is provided in Table 7-1.

At the baseline visit demographics, medical history, diagnostics, cardiovascular medication and quality of life (QoL) questionnaire ("AFEQT") will be recorded. During the index Phased RFA and all re-do Phased RFA procedures, related variables will be collected including: anticoagulation therapy, general procedure summary, consumables, PV isolation confirmation, adverse events (AE) assessment and hospital discharge status. During the FU period, information about in-hospital visits will be captured in the "General FU" CRFs. The "General FU" CRF contains data about arrhythmia diagnostics, symptoms, hospitalization and cardioversions (from previous visit date to actual visit), re -ablation information, cardiovascular medication, and AE assessment.

At 12 months FU, patients will be either followed up in the medical center ("12 months FU") or by phone ("12 months FU by phone"). Data recorded on the "12 month follow up" CRF is equivalent to the "General FU" CRF, with the addition of the QoL questionnaire (AFEQT). If patient has no reason to visit the medical center between 12 and 13 month after the index procedure, he might be called by study personnel and asked questions for about 15-20 min about any AF symptoms, hospitalizations, AF cardioversions since the previous visit, current medications and quality of life. Whenever 12 months FU performed by phone, data received via CareLink may be used for confirmation of rhythm disturbances. The interview does not replace a medical checkup for the patient and serves as data collection only.

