## 3 Study Design

### 3.1 Design

The GOLD RF registry is a postmarket release (PMR), prospective, observational, multi-centre, clinical study in consecutive subjects with atrial fibrillation treated with the phased RFA technology (Medtronic, Minneapolis, MN, USA). Patient's participation in this study has no impact on his or her indication, diagnostics or therapy. Subjects are supposed to be treated in compliance with current valid Instructions for Use (IFU) as well as according to medical society guidelines and the clinic's internal directives. Medication-based therapy should also meet medical society guidelines or the clinic's internal directives, respectively.

[figure not shown]
40 sites in 14 countries (Germany, Netherlands, United Kingdom, Hungary, Italy, Spain, Switzerland, Israel, Poland, Portugal, France, Greece, Georgia and South Korea) are anticipated to take part in the registry to get documentation on at least 800-1000 patients (for more details regarding sample size consideration, see Section 3.3 in the SAP). Eligible for participation are study sites and hospital-based physicians treating AF subjects with phased RFA technology. The enrolment period is estimated to be 24 months. The individual observation period per patient is up to 12 (+2) months: Based on the observational plan, it is planned that the baseline visit is conducted by the investigators. All follow-up visits in the registry are unscheduled. They will be conducted in accordance with "routine clinical practice" in the participating medical centres: Between the procedure date and the following 12MFU period, any general FU will be captured. General FUs might occur due to site specific visit schedule, related to AF re-occurrence (re-ablation, AF symptoms, CV etc.) or due to patient visits at the site because of AE related symptoms. At 12MFU window, the patient will either be followed up in the medical centre or by phone.

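### SAP 8.1.1 defines AF re-occurrence by four items, but Tables 4–6 state none of their duration, ECG/EGM or symptom conditions and map no cardioversion field, so the 12-month rate may not be that of the stated endpoint

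*SAP*

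**What the plan says.** SAP 8.1.1 gives a closed list of four events:

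- "AF pharmacological and/or electrical CV"
- "AF more the 30 sec on ECG/EGM"
- "AF less than 30 sec in combination with AF symptoms"
- "Re-ablations for AF"

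The same section then says that the first event and its date come from the eCRF fields listed in Tables 4 (General FU and in-hospital 12-month forms), 5 (12-month phone form) and 6 (AE form). One of these fields is "Reason for visit: AF re-occurrence", dated at the visit. Others are AF in the arrhythmia history since the last visit and AF as a reason for cardiovascular hospitalisation.

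SAP 8.1.2 treats the table entries as the events. It drops those in the first 90 days and takes the first documented date as the event date. (It cites Tables 5 to 7; Table 7 is the safety table, so Tables 4 to 6 are evidently meant.) For the main objective, adjudication is mentioned only for AE data. SAP 7.2.3 keeps events even when a General FU form is discarded.

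On where the ticks come from, SAP 3.1 says a general follow-up may be "related to AF re-occurrence (re-ablation, AF symptoms, CV etc". Protocol 3.4 says a patient followed by phone is "asked questions for about 15-20 min about any AF symptoms, hospitalizations, AF cardioversions since the previous visit, current medications and quality of life", and that "data received via CareLink may be used for confirmation of rhythm disturbances".

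**The concern.** The definition and the derivation sit in one section and describe different endpoints. A programmer working from Tables 4–6 would count an AF visit, an AF history tick or an AF admission without asking whether the episode exceeded 30 seconds on a recording or was shorter with symptoms. The same programmer would find no row for cardioversion, although it heads the definition.

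The 12-month success rate is the registry's main result, and it is also planned by AF type and in Cox models for the subgroups. If it mixes documented recurrence with unconfirmed reports, it is not the rate of the named endpoint. The mix could also differ between patients seen in hospital and patients interviewed by phone, whose forms feed one estimate.

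**Working it through.** **Step 1. Set the rows against the definition.**

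| Field in Tables 4–6 | Table | Item it could serve | Condition stated |
|---|---|---|---|
| Visit reason: AF re-occurrence | 4 | none directly | none |
| Re-ablation for AF (reason or history) | 4, 5 | re-ablation | none needed |
| History of AF since last visit | 4, 5 | AF over 30 s, or shorter with symptoms | no duration, ECG/EGM or symptom condition |
| Hospitalisation for AF | 4, 5 | none; not in the definition | none |
| Free-text AF on AE form | 6 | AF over 30 s, or shorter with symptoms | none in the row; AE data are adjudicated or coded |
| (no row) | – | cardioversion | not mapped |

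Only the re-ablation rows meet the definition as they stand. The mismatch runs both ways: some rows are broader than the definition, and one item has no row.

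**Step 2. Look for a later filter.** SAP 8.1.2 removes entries up to day 90 and nothing else. Adjudication does not extend to the follow-up or phone fields. Symptoms are collected at follow-up, but no symptom field is mapped to the endpoint.

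**Step 3. Illustrate the size.** The plan gives no figure on this point, so there is none to reproduce. Inputs:

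- S, success under the written definition: 74%, from Protocol 4.4.1. This is the predicate platinum catheter's average at a mean follow-up of 10 months, so it is borrowed.
- f, the share of truly event-free patients flagged after day 90 only by a non-qualifying tick: assumed.

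Reported success = S × (1 − f); fall = S × f.

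| f | 74% × (1 − f) | Fall at S = 74% | Fall at S = 80% |
|---|---|---|---|
| 1% | 73.3% | 0.7 points | 0.8 points |
| 2% | 72.5% | 1.5 points | 1.6 points |
| 5% | 70.3% | 3.7 points | 4.0 points |
| 10% | 66.6% | 7.4 points | 8.0 points |

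**Step 4. Allow for the opposite error.** Let g be the share of true failures whose only qualifying event is a cardioversion and who carry no Table 4–6 tick. Reported success is then S × (1 − f) + (1 − S) × g. The two errors cancel when g = f × S / (1 − S) = f × 0.74 / 0.26 = 2.85 × f. That is g = 2.8%, 5.7%, 14.2% and 28.5% for f = 1%, 2%, 5% and 10%. Neither f nor g is in the documents. Some cardioversions will be caught through an AF history or admission tick, which lowers g by an unknown amount.

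**The case against.** The strongest reply is that Tables 4–6 give only labels and field numbers. The content of each field is in the annotated eCRF (SAP Appendix E), which was not in the text reviewed, so a 30-second or ECG condition inside a field cannot be ruled out. The tables can also be read as showing where an already defined event and its date are found, not as replacing the definition. Both points stand, and they are why the conclusion is that the rate *can* depart from the definition. They do not remove the need for the SAP to say which rule governs.

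A reader might infer more than the documents support:

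- *That a patient with palpitations and sinus rhythm is counted as an event.* SAP 3.1 describes why general follow-ups may occur. It is not a coding rule for the visit-reason field.
- *That phone reports are confirmed only through CareLink.* Protocol 3.4 makes CareLink optional, but Protocol 7.2 and Table 7-1 also have diagnostics collected at the phone contact.
- *That success is understated by about as much as the planned precision.* The share f is assumed, and many AF visits and admissions will meet the definition. The ±3.8% in SAP 3.3 refers to a 20% re-ablation proportion. It also does not reproduce: 1.96 × √(1.2 × 0.2 × 0.8 / 800) = 3.04%.
- *That a recorded qualifying item should simply be required for every main event.* Visits are unscheduled and no extra tests are required, so this could turn true but undocumented recurrences into event-free cases, mostly among phone patients.

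Counting all reported AF is a defensible conservative choice in a descriptive registry, provided it is labelled as such.

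**Conclusion.** The mismatch is real on the face of the SAP. After day 90, Tables 4–6 can count reports that do not meet the four-item definition, and they may miss cardioversions that do. The first error lowers reported success: by 0.7 to 7.4 points for f from 1% to 10% at S = 74%. The second raises it, and the net direction is uncertain. The figures rest on an assumed f and a borrowed S and show scale only. A downward bias in the reported rate is not established, and the conclusion is subject to whatever conditions the annotated eCRF fields contain. The plan should be changed because its main result must be tied to one stated endpoint, and the change is cheap.

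**What to change.** In SAP 8.1.1:

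1. State that the four-item definition governs.
2. Map the cardioversion, ECG/EGM, duration and symptom fields where the eCRF captures them. Protocol 3.4 has cardioversions on the General FU form and in the phone interview; Protocol Table 7-1 has diagnostics and symptoms on all three follow-up forms.
3. Classify each Table 4–6 tick as either *meets definition* or *reported, unconfirmed AF*.
4. Present two 12-month Kaplan–Meier estimates side by side: events meeting the definition, and all reported AF.
5. Show both by in-hospital versus phone 12-month contact in the FAS, where every patient has a valid 12-month form. Keep this descriptive, because the type of contact is settled after the procedure.
6. If the eCRF does not capture episode duration, say so and label the endpoint as reported AF recurrence.

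The cost is SAP wording and extra programming on data already collected. The definition-only estimate may miss true undocumented recurrences, especially in phone patients. That is why both estimates are needed and neither should be shown alone.
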